## Progression-free survival

Progressive disease is defined by the tumour growing significantly or new tumours appearing. Progression-free survival is defined as the time from date of trial entry to date when progression is first observed and is censored at date last seen free of local recurrence in those patients who have not experienced the event.

## Overall survival

Overall survival is defined as the time from date of trial entry to date of deaths from any cause and is censored at date last seen alive in those patients who have not experienced the event.

## 14.2 Statistical analysis

The main analysis will be carried out when all patients have completed their neoadjuvant therapy and have had their assessment of response. The main analyses comparing the objective clinical response rates will be carried out with and without adjustment for the additional randomisation; e.g. in the 500 patients receiving celecoxib vs 500 patients receiving celecoxib-placebo, objective clinical response rates will be assessed using the chi-squared test, and repeated using the Mantel-Haenszel test to allow for the adjustment of exemestane or letrozole. An additional pre-planned analysis will be the comparison of the 250 patients in each of the 4 treatment groups using one test statistic; this will be powered to detect larger differences (~13%). We do not plan to carry out multiple comparisons between the 4 treatment groups, instead we will perform one test statistic to determine if there are differences between any of the 4 treatment groups.

The secondary outcomes of survival and local control will be assessed using Kaplan-Meier survival curves, and treatments will be compared using the Log-rank test. The effect of

prognostic factors in addition to treatment will also be assessed using Cox-regression models. All analyses will be carried out on an intention-to-treat basis.

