### RANDOMISATION

(9:00am till 5:00pm, Monday to Friday)

☎ [name] or [name]

✉ [name]

During the randomisation procedure eligibility criteria and randomisation details will be confirmed and verification that the patient has signed the NEO-EXCEL Informed Consent Form will be requested. A unique sequential Trial Number (TNO) will be allocated. This number should be used on all Case Report Forms (CRFs) and all subsequent correspondence relating to that patient. The TNO and allocated treatment must also be recorded on the Randomisation Form, and the Form then signed and dated. The completed original Forms should be sent to the NEO-EXCEL Study Office, with copies retained at site. Confirmation of the randomised treatment allocation will be sent to the Investigator and appointed Pharmacist.

Randomisation will be stratified by tumour size (>2-5cm, >5cm), grade (I, II, III), ER Q-score (3-4, 5-6, 7-8), Her2 (-ve, +ve, not determined), and low dose aspirin use (yes, no). This information therefore must be available at randomisation. A computerised minimisation algorithm, developed by the Trials Unit, will be used to ensure that allocation of treatment to patients is balanced within these strata.

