## 8. TREATMENT DETAILS

### 8.1 Trial plan

**Treatment should begin within 5 working days of randomisation. The planned duration of treatment is 16 weeks.**

## **Subjects will be randomised (1:1:1:1) to receive either:**

### **Exemestane + Celecoxib**

Patients will receive exemestane 25mg, one tablet daily and celecoxib 400mg, one capsule twice daily

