### **14.3 Sample size**

The trial will accrue a total of 1000 patients.

The objective clinical response rate for patients receiving letrozole is reported to be around 55%, thus randomising 250 patients into each of the 4 treatment arms will allow the detection of an absolute difference of 13% between any of the treatments, with 5% significance and 85% power (Machin and Campbell 1987). Within the 2x2 factorial design, the comparison of the 500 patients receiving celecoxib vs 500 patients receiving placebo will allow the detection of an absolute difference of at least 9% with an 80% power; similarly for 500 patients receiving exemestane vs the 500 patients receiving letrozole. Recruiting 1000 patients will also allow the comparison of the secondary endpoints of type of surgery and biological profiling as well as correlating objective clinical response with overall survival and local control.

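### The main response tests in Section 14.2 leave out the five minimisation factors: a modest loss of efficiency if those factors are prognostic, and no threat to validity

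*Protocol*

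**What the plan says.** Protocol Section 7 lists the first four allocation factors: "Randomisation will be stratified by tumour size (>2-5cm, >5cm), grade (I, II, III), ER Q-score (3-4, 5-6, 7-8), Her2 (-ve, +ve, not determined". The fifth factor is whether the patient takes aspirin at low dose (two levels). On the method, the section says: "A computerised minimisation algorithm, developed by the Trials Unit, will be used to ensure that allocation of treatment to patients is balanced within these strata". Section 8.1 gives the ratio: "Subjects will be randomised (1:1:1:1) to receive either" one of the four combinations, so each factorial comparison sets 500 patients against 500.

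Section 14.2 says of the primary endpoint: "The main analyses comparing the objective clinical response rates will be carried out with and without adjustment for the additional randomisation". Its worked example is celecoxib against placebo, where "response rates will be assessed using the chi-squared test, and repeated using the Mantel-Haenszel test to allow for the adjustment of exemestane or letrozole". The only adjustment variable is therefore the other randomised drug. Prognostic factors come up once in that section, in the sentence on Cox models that follows the survival and local control outcomes.

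Section 14.3 says: "The objective clinical response rate for patients receiving letrozole is reported to be around 55" per cent. It claims 80% power for a 9-point difference in each factorial comparison.

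**The concern.** Minimisation makes the arms more alike on the chosen factors than simple randomisation would. Where those factors predict response, the difference in response rates varies less from trial to trial. A chi-squared test still uses the variance that applies under simple randomisation. Its standard error is then too large, its confidence interval too wide and its actual size below 5%. An analysis that includes the factors recovers the lost precision.

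The Mantel-Haenszel repeat cannot do this, because it stratifies by the other drug and not by the minimisation factors. The two analyses are also both described as main, and the section does not say which decides.

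At stake is some power, and a p-value and interval that match the way patients were allocated.

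**Working it through.** **Inputs.** From Sections 8.1 and 14.3: 500 v 500, control rate 55%, difference 9 points (55% v 64%), significance 5%. The protocol does not state sidedness, so two-sided is assumed.

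**1. The plan's own figure.** Pooled rate = (0.55 + 0.64)/2 = 0.595.
- Null SE: se0 = √(0.595 × 0.405 × 2/500) = 0.03105.
- Alternative SE: se1 = √((0.55 × 0.45 + 0.64 × 0.36)/500) = 0.03092.
- Power = Φ((0.09 − 1.96 × 0.03105)/0.03092) = Φ(0.943) = 82.7%.

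With continuity correction it is 81.0%. The stated 80% is reproduced and lies slightly on the safe side.

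**2. Effect of leaving the factors out.** Let R2 be the share of outcome variance explained by the minimisation factors. The large-sample formulas, which assume that balance on the factors is essentially complete, are:
- Actual size of the unadjusted test: P(|Z| > 1.96/√(1 − R2)).
- Unadjusted power: Φ((0.09 − 1.96 se0)/(se1 √(1 − R2))).
- Adjusted power: Φ((0.09 − 1.96 se0 √(1 − R2))/(se1 √(1 − R2))).

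Example at R2 0.10, where √0.9 = 0.9487:
- Size = P(|Z| > 2.066) = 3.9%.
- Unadjusted power = Φ(0.02915/0.02933) = Φ(0.994) = 84.0%.
- Adjusted power = Φ(0.03227/0.02933) = Φ(1.100) = 86.4%.

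| R2 (assumed) | Size, unadjusted | Power, unadjusted | Power, adjusted |
|---|---|---|---|
| 0 | 5.0% | 82.7% | 82.7% |
| 0.02 | 4.8% | 83.0% | 83.5% |
| 0.05 | 4.4% | 83.3% | 84.6% |
| 0.10 | 3.9% | 84.0% | 86.4% |
| 0.20 | 2.8% | 85.4% | 90.1% |

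**3. Simulation.** Each trial had 1000 patients and four-arm minimisation on the five factors. The factor prevalences, the effect sizes and a 90% deterministic allocation rule were assumed. There were 2500 to 3000 trials per setting. The Monte Carlo SE is about 0.4 points for size and 0.7 for power.

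| R2 | Chi-squared: size, power | Adjusted logistic: size, power |
|---|---|---|
| 0 | 5.5%, 83.0% | 5.4%, 83.2% |
| 0.03 | 4.2%, 81.7% | 4.5%, 83.0% |
| 0.10 | 4.6%, 84.3% | 5.3%, 87.2% |
| 0.18 | 3.7%, 85.0% | 5.6%, 89.2% |

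The direction agrees with the formula. Only at R2 0.18 is the simulated size of the chi-squared test clearly below 5%, so the conservatism at smaller R2 rests on the formula.

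**4. The Mantel-Haenszel repeat.** Its rejection rates were within 0.1 point of chi-squared in every setting. The simulation gave the other drug no effect, but a real effect would change little. A balanced two-level factor with a 9-point effect explains 0.09²/4 = 0.0020 of a variance of about 0.24, which is under 1%.

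**5. Evidence on R2 in the protocol.** Section 3.2.1 gives response rates of 15/17 in HER-1/HER-2-positive tumours (the text implies letrozole) and 55/101 on letrozole in negative ones. The overall rate is 70/118 = 0.593, with variance 0.241. The between-group variance is (17/118)(101/118)(0.882 − 0.545)² = 0.014. R2 is then about 0.014/0.241 = 0.06. This rests on 17 tumours and on a marker group that includes HER-1, which is not a minimisation factor, so it is indicative at most.

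**The case against.** The strongest reply is that nothing is broken. Chi-squared and Mantel-Haenszel are valid here, they match the two-proportion sample size calculation, and the 80% power is met without adjustment. That stands. A reader might infer from the mismatch between allocation and analysis that the false-positive rate is inflated or the trial underpowered. The calculations show neither: any error in size is on the conservative side.

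A reader might also infer from Section 3.2.1 that response is known to vary strongly with ER score and HER status. The text does not support that. It describes the ER pattern as most marked on tamoxifen, which is not a trial treatment, and as not statistically different, with few tumours at low scores. Its p = 0.004 sets 4/19 on tamoxifen against 15/17. That is a contrast between drugs, not a prognostic effect among patients on an aromatase inhibitor.

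Nor does having two main tests open a real choice of result. They will nearly always agree, and the wording suggests that chi-squared comes first. Naming one deciding analysis is tidier but changes little.

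Finally, the choice of covariate model is often left to a statistical analysis plan, and none was available for this review. That is fair for model details. But Section 14.2 already names the tests and the single adjustment variable, so the point rests on stated text and not on silence.

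**Conclusion.** The point holds as a modest matter of efficiency. Section 14.2 omits from the main response tests all five factors used to allocate treatment, and the one adjustment it does make recovers almost nothing.

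The cost depends wholly on an R2 that the documents do not supply. There is none if the factors are not prognostic. By the large-sample formula the loss is about 1 power point at R2 0.05, between 2 and 3 at 0.10 and between 4 and 5 at 0.20. The actual size falls to about 4.4%, 3.9% and 2.8% respectively.

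These figures assume a two-sided 5% test, 500 v 500, 55% v 64%, and near-complete balance on the factors. Some of the gain in the simulation may reflect the adjusted test running at 5.3% to 5.6% in the two stronger settings, although that is within about 1.5 Monte Carlo SE of 5%.

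**What to change.** In Section 14.2, name one primary analysis for each factorial comparison: a logistic regression of response on both randomised drugs plus the five minimisation factors as main effects, with the values recorded at randomisation. Report the odds ratio and a standardised risk difference with 95% CI. State in advance how sparse factor levels will be merged. Use main effects and not full stratification, since the factors define 2 × 3 × 3 × 3 × 2 = 108 cells, or about 9 patients per cell. Keep the chi-squared and Mantel-Haenszel tests as supportive analyses.

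The cost is a slightly more complex model and the need to write the merging rule. No extra patients, visits or data are needed, because Section 7 already requires all five factors to be known at randomisation.

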### **14.3 Sample size**

The trial will accrue a total of 1000 patients.

The objective clinical response rate for patients receiving letrozole is reported to be around 55%, thus randomising 250 patients into each of the 4 treatment arms will allow the detection of an absolute difference of 13% between any of the treatments, with 5% significance and 85% power (Machin and Campbell 1987). Within the 2x2 factorial design, the comparison of the 500 patients receiving celecoxib vs 500 patients receiving placebo will allow the detection of an absolute difference of at least 9% with an 80% power; similarly for 500 patients receiving exemestane vs the 500 patients receiving letrozole. Recruiting 1000 patients will also allow the comparison of the secondary endpoints of type of surgery and biological profiling as well as correlating objective clinical response with overall survival and local control.

### **14.4 Timing of interim and final analyses**

The first interim analysis will be carried out and presented to the Independent Data Monitoring Committee (IDMC) after 400 patients have been recruited into the trial. This analysis will assess recruitment, toxicity, compliance, number of adverse/treatment related events and response. It is anticipated that interim analyses will be carried out and presented to the IDMC annually thereafter. See Section 10.8 for further details. The final analysis and publication of results for all outcomes except time-to-event measures, will be carried out once all randomised patients have completed surgery. The final analyses and publication for time-to-event outcome measures will occur when all randomised patients have a minimum of 2 years follow-up and again at a minimum of 5 years follow-up.

## **15. ETHICAL AND REGULATORY STANDARDS**

### **15.1 Ethical / Regulatory conduct of the study**

This study will be conducted in accordance with the recommendations guiding physicians in biomedical research involving human subjects, adopted by the 18th World Medical Association (WMA) Declaration of Helsinki (1964) and the Tokyo (1975), Venice (1983), Hong Kong (1989), South Africa (1996) and Scotland (2000) amendments (Appendix 3).

This study will be carried out under a Clinical Trial Authorisation (CTA) and conducted in accordance with EU Directive 2001/20/EC and UK legislation.

The protocol will be submitted for ethical approval prior to circulation, in accordance with the new guidance in force from March 1st 2004. Before enrolling patients into the study, each site must apply for Site Specific Assessment from their Local Research Ethics Committee and must also obtain Trust Research & Development (R&D) approval. Sites will not be permitted to enrol patients until written confirmation of ethical and R&D approval is received by the NEO-EXCEL Study Office. It is the responsibility of the Investigator to ensure that all subsequent amendments

gain the necessary approval. This does not affect the individual clinicians' responsibility to take immediate action if thought necessary to protect the health and interest of individual patients.

## **15.2 Informed Consent**

It is the responsibility of the local Investigator to obtain fully Informed Written Consent from each patient prior to inclusion in the trial or, where relevant, prior to evaluating the patient's suitability for the trial. The approved Patient Information Sheet should be given to each patient prior to randomisation, with the risks and benefits of participating in the trial clearly explained. The patient should be given ample time to read the information sheet and the opportunity to inquire about details of the trial. They should also be given time to discuss their participation with others outside of the clinical trials team and given another opportunity to ask the clinician and the research nurse questions regarding their participation in the study if required. All questions or concerns about the trial should be answered to the satisfaction of the patient. Sufficient time should be allowed (at least 24 hours) for the patient to reach a decision. It should be explained that they are free to refuse to take part and informed about their right to withdraw from the trial at any time. If the patient agrees to take part in the trial they should be asked to sign and date the approved Informed Consent Form, which should also be signed and dated by the Investigator. A copy of the Informed Consent Form should be given to the patient, a copy filed in the hospital notes and a copy filed in the Investigator Site File. Throughout the study the patient should have the opportunity to ask questions about the trial and any new information that may be relevant to the patient's willingness to continue participation in the trial should be shared with the patient in a timely manner.

The Informed Consent Form and Patient Information Sheet will be available in electronic format from the NEO-EXCEL Study Office to enable individual hospitals to copy onto their headed paper. A copy of the Informed Consent Form and Patient Information Sheet is included in Appendices 7 and 8 for information. The Breast Biopsy Patient Information Sheet and Consent is included in Appendices 9 and 10.

With the patient's consent their General Practitioner (GP) should be informed about their participation in the trial. The approved GP Information Letter (Appendix 11) should be sent to the GP, along with any other related correspondence.

## **15.3 Patient confidentiality**

The personal data recorded on all documents will be regarded as strictly confidential and will be handled and stored in accordance with the 1998 Data Protection Act. With the patient's consent, their full name will be collected at randomisation to allow tracing through the Office of National Statistics to assist with long-term follow-up. However, patients will be identified using only their unique trial number, initials, hospital number and date of birth on all CRFs and any correspondence between the NEO-EXCEL Study Office and the participating site.

The Investigator must maintain documents not for submission to the Study Office (e.g. patients' written Informed Consent Forms) in strict confidence. In the case of special problems and/or governmental queries, it will be necessary to have access to the complete study records, provided that patient confidentiality is protected.

The Cancer Research UK Clinical Trials Unit, Birmingham will maintain the confidentiality of all patient data and will not disclose information by which patients may be identified to any third

party, other than those directly involved in the treatment of the patient's breast cancer. Representatives of the trial team may be required to have access to patient notes for quality assurance purposes but patients should be reassured that their confidentiality will be respected at all times.

## 16. TRANSLATIONAL SCIENCE

Whilst there is extensive in vivo and in vitro data to suggest that inhibition of the COX 2 mediated synthesis of prostaglandins may promote tumour response and prevent tumour spread, there is no clear consensus as to the relevant mechanisms and their relative importance. Early experimental evidence suggests that prostaglandin E2 (PGE2) expression is elevated in breast cancer and that this is associated with tumour invasion. Prostaglandins are implicated in a wide range of molecular actions including: the induction of interleukin6 (IL-6) and other inflammatory cytokines, neo-vascularisation and tumour invasion/proliferation. The rationale for linking COX 2 inhibitors with aromatase inhibitors in endocrine-responsive disease is due to the action of PGE2, mediated via the 1.3 promoter of the aromatase gene itself and leading to enhanced aromatase expression as a direct consequence of COX 2 activity. Given the increasingly widespread use of celecoxib as a novel anti-tumour agent there is a strong need for a clearer understanding of the mechanisms by which COX 2 mediates its actions in vivo. NEO-EXCEL represents an ideal opportunity to investigate this question and to provide strong evidence for predictive factors that may be used to inform future treatment decisions.

As a secondary objective, we intend to exploit the tissue collected by the NEO-EXCEL study to investigate expression profiles relating to tumour response to steroidal (exemestane) versus non-steroidal (anastrozole/letrozole) aromatase inhibitors. Patients with metastatic disease who have progressed after treatment with non-steroidal inhibitors (anastrozole and letrozole) have been treated with exemestane. Of 241 patients treated, 24% experienced clinical benefit (CR + PR + SD) lasting for a median time of 37 weeks. This suggests that there is a degree of non cross-resistance between these classes of aromatase inhibitors. Secondly, there appear to be differences between the molecular profiles of tumours responsive to steroidal irreversible (exemestane) and non-steroidal reversible inhibitors of aromatase, as suggested by data presented at the San Antonio breast cancer symposium^54. We therefore propose, within NEO-EXCEL, to establish a tissue and serum bank for future gene expression profiling and proteomic analysis to answer two key questions. Firstly and most importantly, we hypothesise the expression profiling of sequential tumour biopsies will identify molecular mechanisms which underpin the effects of the COX 2 inhibitor celecoxib in the context of neoadjuvant therapy of breast cancer. Secondly, we further hypothesise that markers of differential response to aromatase inhibitors will be identified in a linked analysis.

Our aim is to collect three sequential tumour samples (pre-treatment, 2 weeks after therapy initiation and at surgery) from patients randomised between the different aromatase inhibitors and also between celecoxib and placebo; these timepoints have been chosen to link to previous studies (Dixon et al, Dowsett et al) of early response to hormone therapy. We also aim to analyse, in a subset of patients (participating in the frozen tissue sub-protocol), sequential tumour biopsies and the changes in Gene Expression Profiles (GEPs) of breast tumours from each treatment arm to determine, at the level of gene expression, the molecular differences induced in tumours during treatment with exemestane and letrozole +/- celecoxib combination therapy. We predict that a number of the identified differentially expressed genes will serve as useful response markers for adjuvant studies (e.g. TEAM/ATAC). A significant change post treatment

may provide useful candidate response markers in the context of neoadjuvant treatment, which may be profiled in the wider tumour databank (tissue microarrays) from the NEO-EXCEL trial.

It is now clear that only a small number of genes are up-regulated in all breast tumours. Furthermore, while single genetic markers in clinical specimens have often failed to be predictive of prognosis, recent studies have demonstrated that the GEP of multiple genes in combination can predict the response to tumours in terms of outcome and can provide prognostic and response information.

Affymetrix human GeneChip microarrays will be used to undertake this analysis, each containing oligonucleotides representing more than 39,000 transcripts derived from approximately 33,000 well-substantiated human genes. Such a set will include the majority of genes whose expression changes have been shown in the above studies to be relevant to the development or progression of different types of breast cancer. We propose to select 100 patients (50 patients from each treatment group) to yield 300 samples for expression array analysis. Our aim is to collect this material during the course of recruitment and to bank this material in a central laboratory prior to submission of a TRICC translational science project or CRUK project grant for the expression profiling of this material in conjunction with the CRUK Genome Profiling Laboratory at the Paterson Institute. Subsequently the predictive value of genes shown to be linked to tumour response from the study will be tested using material collected as formalin fixed tissue from the remainder (900 cases + 100 entered into the profiling sub-study). These profiles may also inform the analysis of samples in TRANS-REACT and TRANS-MA27.

